Part 2 is an open-label, long-term safety study of ZX008 for subjects who have successfully completed 14 weeks of treatment (titration + maintenance) in Part 1 and are candidates for continuous treatment for an extended period of time; subjects who have not completed the entire 14 weeks of treatment in Part 1 may be eligible to participate in Part 2 on a case-by-case basis and only following sponsor approval. Part 2

Version 2.0

Syneos Health #1009529A

consists of a 12-month Open-Label Extension (OLE) Treatment Period and a 2-week Post-Dosing Period. Thus, subjects who were randomized to ZX008 during Part 1 and complete Part 2 will have been treated with ZX0008 for at least 70 weeks (including their participation in both Part 1 and Part 2).

During Part 2 all subjects are treated initially with 0.2 mg/kg/day for 1 month to assess effectiveness of this dose in all study subjects. After 1 month at a dose of 0.2 mg/kg/day, the investigator may adjust the dose for each subject based on effectiveness and tolerability. Dose changes should be made in increments of 0.2 mg/kg/day, to a maximum of 0.8 mg/kg/day (or 0.5 mg/kg/day for subjects taking concomitant STP) but not to exceed total dose of 30 mg/day (or 20mg/kg/day for subjects taking concomitant STP). During the 12-month OLE subjects will have ECG and ECHO assessments at months 1, 3, 6, and 9, and at the end of study visit.

A follow-up ECG and ECHO will be performed at 3 and 6 months after study drug discontinuation for early termination and for those subjects who complete Part 2. Subjects enrolled in Germany, France and Netherlands will have an additional follow-up at 24 months. If there are any findings at a post-dose follow-up, another follow-up will scheduled every 3 months until resolved or stabilized. In both Part 1 and Part 2 parents/caregivers will use a diary every day to record the number of seizures, type of seizures, time and duration of seizures, whether the seizure resulted in a drop, dosing of study drug, and use of rescue medication.

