Placebo	Placebo	Placebo	Placebo		

After completion of the Titration Period, subjects enter the Maintenance Period and continue to receive the randomized dose of ZX008 or placebo and be treated for an additional 12 weeks.

Subjects who complete the Maintenance Period and do not be continue into Part 2, the open-label extension, and subjects who discontinue from Part 1 early, will be tapered off of study medication as outlined in Table 2.

Table 2: Taper Algorithm for Part 1

Randomized Group	Taper Step 1	Taper Step 2
\C	Day 1-4 after study	Days 5-8 after study
X Y	completion or early	completion or early
-0~	termination	termination
ZX008 0.2 mg/kg/day	Placebo	Placebo
ZX008 0.8 mg/kg/day (0.5	ZX008 0.4 mg/kg/day	ZX008 0.2 mg/kg/day
mg/kg/day for subjects		
taking concomitant STP)		
Placebo	Placebo	Placebo

Subjects who complete the Maintenance Period and will be continuing into the openlabel extension (Part 2) will be transitioned from double-blind study medication to open-label ZX008. All subjects entering the open-label extension (Part 2) will be transitioned from their blinded daily dose to the 0.2 mg/kg/day dose during the 2-week interval between Visits 12 and 15, without breaking the blind. The IWR system will assign two bottles of Investigational Medicinal Product (IMP) to the subject, one for

Version 2.0

Syneos Health #1009529A

each step in the transition. A new bottle of IMP will be started by the subject at each level of the transition step.

Table 3: Transition Algorithm for Part 1

	Tuble 3. Translation Algorithm		
	Dose Group in Double-	Transition Step 1	Transition Step 2
	Plind Ctudy	Day 1 4 after Visit 12	Day 5 14 after Visit 12
	ZX008 0.2 mg/kg/day	ZX008 0.2 mg/kg/day	ZX008 0.2 mg/kg/day
	ZX008 0.8 mg/kg/day (0.5	ZX008 0.4 mg/kg/day	ZX008 0.2 mg/kg/day
	mg/kg/day for subjects		
	Placebo	7Y008 0.2 mg/kg/day	7Y008 0. 2 mg/kg/day/
	1 tacebo	ZX000 0.2 mg/ kg/ day	Z/000 0.2 mg/kg/day
Kilis	The full list and timing of students of the full list and timing of the full list and time time full list and time full lis	ZX008 0.2 mg/kg/day ZX008 0.2 mg/kg/day ZX008 0.2 mg/kg/day dy procedures is provided in Tab	ole 4.
,	This documer 03.007A.03	nt is proprietary and confidential to Syr Syneos Health	neos Health Page 19 of 110

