- c: The safety follow-up visit will be conducted for subjects who either terminate early from Part 1, or who complete Part 1 but do not enter Part 2. Standard follow-up visits should occur 3 and 6 months after the last dose. For subjects enrolled in Germany, France and Netherlands, follow-ups will also occur 24 months after the last dose. If there are any findings at the last post-dose follow-up, a follow-up visit will be repeated every 3 months until resolved or stabilized.
- d: The Visit 8 ECHO must be performed any time between Study Day 40 and Study Day 54. The Visit 12 ECHO must be performed any time between Study Day 90 and Study Day 113; if a subject discontinues early from the study, the ECHO should be scheduled as soon as practical. If the Study Day 43 ECHO was completed ≤ 30 days prior to early termination, the Visit 12 ECHO will not be performed provided the parent/guardian agrees to bring the subject to the clinic for the cardiac follow-up visit.
- e: Females of child-bearing potential
- f: Plasma sample for pharmacokinetic assessment will be conducted prior to the dose at Visit 8 and 1, 2, and 4-6 hours after dose administration.
- g: Plasma sample for assessment of background AED(s) will be conducted prior to the dose of AED(s) at Visits 3, 8 and 12 (Visits 6 and 10 only if clinically indicated). AED plasma sample may be collected after the morning dose of AEDs are taken, if preferable, as long as the time of last dose is accurately recorded.
- h: Study drug/diary dispensed for the Transition Period for subjects entering the open-label extension and for the Taper Period for subjects exiting the study.
- i: Site personnel will review study medication dosing procedure (titration) with parent/caregiver.
- j: Study drug administration begins in the morning of Study Day 1. Study Day 1 is considered the first day of dosing, even though subjects may receive an in-clinic dose on Study Day -1. If the first dose is taken in the clinic, it will be recorded in the eCRF, but not the subject diary; the next dose on the morning of Study Day 1 will be the first entry in the subject's diary.
- k: Only adverse events related to cardiac safety will be collected at this visit.
- 1: Visit 13 may be conducted as a phone call, provided diaries and study medication are returned by this time.
- m: An abbreviated physical and/or neurological examination to be conducted as appropriate based on last exam and reported AEs.

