- n: Randomization should not occur prior to receiving approval from the Epilepsy Study Consortium and ERT ECHO results.

This document is proprietary and confidential to Syneos Health

Syneos Health

Page 23 of 110

					Part 1 As	sessment	s			4	0	.01)	
Study Assessments – PART 1	Basel	ine Peri	od ^a			Titra	tion + Ma	intenance	Period	XI		To a:		Cardia
Visit Number	Screening		Random- ization	Ti	itration Po	eriod	Maintenance Period			Period	SIL	EOS/	Doginal	
	1	2 (Phone)	3		4, 5 (Phone)	6	7 (Phone)	8	9 (Phone)	10	11 (Phone)	12	13	14
Study Day	-28	-15	-1	1	4, 8	15	29	43	57.	71	85	99	113	197
			Q	JY	7,40) (\$10"							
Study Day O: Urine for urinalysis may be colle 3.007A.03	્ હ	SINN	of po	15	so si	He.								

Urine for urinalysis may be collected at home, the night before the clinic visit, as long as collection procedures are followed to maintain sample stability.

Table 5: Visit windows for Part 1 Visits

The targeted study day and allowable windows for visits in the protocol below. Early termination visits will be mappe windows.	
Table 5: Visit windows for Part 1 Visits	
	Time window (relative to
	scheduled visit /
Visit / Procedure	procedure)
Visit 1 (Clinic; Study Day -29 to -28 or -28 to -27):	Not Applicable
Visit 2 (Phone; Study -15)	± 3 days
Visit 3 (Clinic; Study Day -1; Randomization	± 4 days ^a
Visits 4, 5 (Phone: Study Days 4, 8)	± 3 days
Visit 6 (Clinic; Study Day 15)	± 4 days
Visit 7 (Phone; Study Day 29)	± 4 days
Visit 8 (Clinic; Study Day 43)	± 4 days
Visit 9 (Phone: Study Day 57)	± 4 days
Visit 10 (Clinic; Study Day 71)	± 4 days
Visit 11 (Phone: Study Day 85)	± 4 days
Visit 12 (Clinic: Study Day 99)	± 4 days
Visit 13 (Clinic; Study Day 113; post dosing)	± 4 days
Visit 14 (ECHO clinic; 3-24 months after last dose) ^b	+ 30 days

AED=antiepileptic drug (s); ECHO=echocardiogram;.

5. **ENDPOINTS**

PRIMARY EFFICACY ENDPOINT 5.1.

Percent change from baseline in the frequency of seizures that result in drops (DSF) in the combined Titration and Maintenance Periods (T+M) in the ZX008 0.8 mg/kg/day group compared to the placebo group. Seizures that results in drops are GTC, SGTC, TS, AS, and TA confirmed for each subject as a drop seizure by the ESC.

KEY SECONDARY EFFICACY ENDPOINTS

The key secondary endpoints are:

a In cases where the screening period is extended beyond 28 days, the immediate 28 days before the Randomization visit will be used to calculate the baseline seizure frequency

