Taper/Transition Period	The Taper/Transition period consists of 2 weeks starting from end of study/early termination visit (Visit 12) + 1 day through Visit 13 (Taper) or Visit 15 (Transition to Part 2). For subjects who are not entering into the Part 2 of the study, subjects will gradually be tapered off of study medication. For subjects who are entering Part 2, subjects will enter the transition phase where all subjects will be on a dose of 0.2	
	mg/kg/day at the end of this phase.	

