2.2.1 Cardiovascular Safety Objectives

The primary cardiovascular safety objective of this analysis is to evaluate the effect of ZX008 on the heart as demonstrated by ECHO.

Variables included in the analysis are listed below. These will be compared between Placebo and the 0.2 mg/kg and 0.8 mg/kg groups independently.

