3.2.3 Collection of Echocardiograms

ECHOs in Part 1 were performed at:

- Screening (Visit 1)
- Maintenance Period (Visit 8; between Study Day 40 and 54)
- EOS/ET (Visit 12; between Study Day 90 and Study Day 113)
- Follow-up (Visit 14)
- Unscheduled

The time of the ECHO was not controlled.

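### The end-of-study echocardiogram window runs about two weeks past Visit 12, into days when subjects entering Part 2 have left their randomised dose, and the cardiovascular SAP neither flags nor separates those scans

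*SAP*

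**What the plan says.** The window appears twice, with the same limits. Cardiovascular SAP Section 3.2.3 lists "EOS/ET (Visit 12; between Study Day 90 and Study Day 113", and a footnote to the main SAP's schedule of assessments (Table 4, in Section 4.4) says "The Visit 12 ECHO must be performed any time between Study Day 90 and Study Day 113". The main SAP's visit-window table (Table 5) has "Visit 12 (Clinic: Study Day 99", with ± 4 days. Main SAP Section 6.7 ends Maintenance at Visit 12 and starts Taper/Transition the next day.

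On dosing after Visit 12, main SAP Section 4.4 says "All subjects entering the open-label extension (Part 2) will be transitioned from their blinded daily dose to the 0.2 mg/kg/day dose". In its Table 3, transition days 1–4 put placebo subjects on 0.2 mg/kg/day, keep the 0.2 arm at 0.2 and move the 0.8 arm to 0.4. The second step (headed "Day 5 14 after Visit 12") has all three arms at 0.2. Section 6.7 agrees that at the end of this phase "all subjects will be on a dose of 0.2" mg/kg/day. Subjects who do not enter Part 2 follow the separate taper in Table 2.

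On analysis, cardiovascular SAP Section 2.2.1 says of the ECHO variables: "These will be compared between Placebo and the 0.2 mg/kg and 0.8 mg/kg groups independently". Section 2.3.1.1 includes the number with trace or worse mitral or aortic regurgitation at end of study, and Section 2.3.1.2 includes mean PASP change at end of study. Results are tabulated by regimen and visit (4.5.2), all available data are used (4.2.1), and grouping follows the treatment actually taken (4.2).

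**The concern.** A comparison with placebo is informative about a drug effect only if the placebo scans were taken off drug and the active scans on the assigned dose. Late in this window, neither holds for subjects entering Part 2. A placebo subject scanned after Visit 12 is on ZX008, and a 0.8 mg/kg/day subject is on 0.4 or 0.2. Nothing in the cardiovascular SAP separates such scans from those taken during Maintenance.

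The rule of grouping by treatment actually taken does not settle it. It does not say whether a placebo subject's scan made on 0.2 mg/kg/day counts as placebo or as 0.2, and the tables are laid out by Part 1 regimen.

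At stake is how a null end-of-study contrast should be read. If a measure responds to the dose being taken at the time, late scans pull the arms together. In a cardiac safety table, that would make a difference harder to see.

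**Working it through.** The plan gives no figure to reproduce for this point. The check is a day-by-day dose calendar.

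Inputs: ECHO window Day 90–113 (cardiovascular SAP 3.2.3); Visit 12 on Day 99 ± 4, so Day 95 to 103 (main SAP Table 5); titration and transition steps (main SAP Tables 1 and 3); first month of Part 2, "During Part 2 all subjects are treated initially with 0.2 mg/kg/day for 1 month" (main SAP Section 4). The 0.8 arm is taken without stiripentol and below the daily cap.

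**Days in the window.** Window length = 113 − 90 + 1 = 24 days. For subjects entering Part 2:

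| Visit 12 on | Randomised dose | Transition days 1–4 (placebo 0.2, low 0.2, high 0.4) | All arms at 0.2 |
|---|---|---|---|
| Day 95 | Days 90–95: 6 | Days 96–99: 4 | Days 100–113: 14 |
| Day 99 | Days 90–99: 10 | Days 100–103: 4 | Days 104–113: 10 |
| Day 103 | Days 90–103: 14 | Days 104–107: 4 | Days 108–113: 6 |

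In the first row the transition ends on Day 109, and Days 110–113 belong to Part 2, still at 0.2. In the nominal row, 4 + 10 = 14 of 24 days come after the randomised dose.

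**Subjects who taper.** In Table 2 the 0.2 and placebo arms both take placebo from the first taper day. The 0.8 arm takes 0.4 on days 1–4 and 0.2 on days 5–8, where the table stops. So on either route the 0.2 and placebo arms do not differ in current dose on any day after Visit 12.

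**Cumulative dose, Visit 12 on Day 99, entering Part 2 (mg/kg).**

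- Day 99: placebo 0; low 99 × 0.2 = 19.8; high 4 × 0.2 + 4 × 0.4 + 91 × 0.8 = 75.2.
- Day 113: placebo 14 × 0.2 = 2.8; low 19.8 + 14 × 0.2 = 22.6; high 75.2 + 4 × 0.4 + 10 × 0.2 = 78.8.
- High minus placebo: 75.2 at Day 99; 78.8 − 2.8 = 76.0 at Day 113.
- Low minus placebo: 19.8 at Day 99; 22.6 − 2.8 = 19.8 at Day 113.

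The contrast in current dose therefore goes to zero late in the window, while the contrast in cumulative dose is almost unchanged.

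**Size of any dilution.** Suppose a measure followed current dose completely and a share p of each arm's end-of-study scans fell on common-dose days. The observed contrast would be about (1 − p) times the on-dose contrast. The documents do not give p, so this cannot be evaluated.

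**The case against.** The strongest reply is that the window matches the plan's own safety convention. Main SAP Section 6.7 runs safety analyses to the end of Taper/Transition, and the main SAP's safety section reports over a 16-week treatment period, which Day 113 nominally closes. That explains why late scans are collected. It does not make a scan on active drug a placebo observation. For adverse events the main SAP recognises this: Sections 9.3 and 9.3.1 split Titration, Maintenance and Taper/Transition, with separate denominators for the later periods. The ECHO analysis has no such split.

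Several other replies stand:

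- The cumulative-dose contrast does not shrink, and the stated primary cardiac outcome is the development of valvular heart disease and pulmonary arterial hypertension (cardiovascular SAP 4.1). Nothing in the documents shows that PASP or trace regurgitation follows the dose of the last few days.
- Of the five main-focus endpoints in Section 2.3.1.1, only one is defined solely at end of study. Several PASP and outflow-tract endpoints are any-time or post-baseline, and these also use the Visit 8 ECHO (Day 40–54), taken on the randomised dose.
- The ECHO analysis is descriptive, with no formal sample size and no multiplicity control (2.4.1, 4.4).
- Section 4.7 allows additional analyses and Listing 2.1 gives raw ECHO data by subject and visit, so the remedy is within reach. But permitting an analysis is not specifying it.

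A reader might go further and infer that the cardiac comparison with placebo as a whole is biased towards no difference, or that some fixed share of it, say a quarter to a half, is lost. The documents support neither. The first would need every measure to follow current dose; the second needs a distribution of scan dates that is not given.

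**Conclusion.** The point holds in limited form. The end-of-study ECHO can be taken up to about 14 days after randomised dosing ends. Among subjects entering Part 2, placebo subjects are then on active drug, and all arms share one dose on 10 of the 24 window days (6 to 14 over the Visit 12 window). The plan neither separates these scans nor says to which treatment they belong.

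The consequence is conditional: possible dilution of the end-of-study contrasts in regurgitation and mean PASP change, for measures that follow current dose. Its size is unknown. For an effect driven by cumulative exposure it would be small. This is a worthwhile low-cost clarification and does not undermine the cardiac safety analysis. The calendar assumes the dosing tables are followed as written.

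There is also a mismatch of wording. Section 4 of the cardiovascular SAP describes treatment for up to 14 weeks (98 days), while the window it analyses extends to Day 113.

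**What to change.** Leave the visit and dosing schedule unchanged. In the cardiovascular SAP:

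1. Flag each end-of-study ECHO by whether it was done on or before the subject's last Maintenance-dose day.
2. Keep the all-ECHO tables and add, beside them, the end-of-study regurgitation and PASP tables restricted to on-dose scans.
3. State that a scan done after Visit 12 in a placebo subject who is in transition is not an on-placebo observation, and say how the rule on treatment actually taken applies to it.
4. Reconcile the Day 113 limit with the statement of up to 14 weeks in Section 4.

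The cost is one derived flag, from dates already needed to apply the stated windows, and a repeat of existing tables. The downside is fewer ECHOs in the restricted set, which is why it should supplement the all-ECHO tables and not replace them.

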3.2.4 Definition of Baseline

The baseline for this study will be the data collected from the ECHOtaken at Screening.

3.2.5 Variables Measured

ing authorization Echocardiograms were evaluated by two cardiologists using DigiView software. Details of the assessment and adjudication process are available in the ECHO operations manual for these studies.

In addition to assessing each valve (Mitral, Aortic, Tricuspid, and Pulmonary) for regurgitation PASP was measured or calculated on each ECHO for pulmonary hypertension.

3.2.6 Clinical Analysis of ECHOs

Each ECHO was read independently by two physicians. A third physician was assigned as an adjudicator. The adjudicator read the ECHO if any of the following discrepancies occurred between the first and second reader:

- · Aortic valve findings were not identical
- Mitral valve findings were not identical
- Left Ventricular Fractional Shortening difference between the two physicians was >5%
- Left Ventricular Ejection Fraction difference between the two physicians was >10%
- PASP difference between the two physicians was >10 mmHa
- Clinical significance of the comparison to previous echo'sbetween the two readers was not identical

3.2.7 Alert Criteria

Echocardiographic alert criteria included:

- ≥ Mild valve regurgitation (aortic or mitral)
- ≥ moderate valve regurgitation (tricuspid or pulmonic)

- Mean mitral valve gradient ≥ 4 mmHg
- Mean aortic valve gradient ≥ 15 mmHg
- Mean tricuspid valve gradient ≥ 4 mmHg
- Peak pulmonic valve gradient ≥ 21 mmHg
- Tricuspid regurgitation jet velocity > 2.8 meters/s with orwithout any findings OR
- One of the following findings in the absence of being able to measure tricuspid regurgitation jet velocity:
 - o Change in right ventricle/left ventricle basal diameter ratio > 1.0
 - o Right ventricular outflow tract flow acceleration time < 100 ms
 - o Dilation of the inferior cava vein (diameter > 21mm and <50% inspiratory collapse) and/or right atrial dilatation
- o Change in the geometry of the interventricular septum in systole entrici.

 -gurgitation veloc
 Systolic Excursion bela

 -gurgitation veloc
 -gurgitation (flattening) with left ventricular eccentricity index >1.1 in systole
 - Early diastolic pulmonary regurgitation velocity > 2.2 m/s
 - $_{\odot}~$ Tricuspid Annular Plane Systolic Excursion below 18 mm or below Z-

4 Statistical Analysis

The statistical analyses of the cardiac safety data are designed to assess the potential cardiotoxicity of ZX008when administered for up to 14 weeks as adjunctive treatment for children and adults with LGS.

4.1 General Principles and Considerations

This section describes the algorithms and conventions that will generally apply to program analyses and to the formatting of the data, as required to perform the proposed summary tabulations and to create the individual subject data listings. Unless otherwise indicated, these specifications will apply to all analyses. For details on the tables and figures that will be created, please refer to Section 5, Tables, Figures, and Listings.

The statistical analysis will be reported using summary tables, figures, and data listings.

ECG and ECHO variables at each time point will be obtained. Changes from baseline will be calculated and compared for the 0.2 and 0.8 mg/kg/day treatment groups to placebo. The primary outcome is the assessment for the development of valvular heart disease and pulmonary arterial hypertension.

Continuous variables will be summarized using descriptive statistics (i.e., total number, mean, standard deviation [SD], minimum, maximum, and 95% CI). Results will be presented to one or two decimal places for means and SD, as appropriate.

Categorical variables will be presented as category counts and percentages. Percentages will be presented to onedecimal place.

All dates will be displayed in DDMMMYYYY format (e.g.,15DEC2012).

All analyses will be carried out using SAS® Version 9.4 or higher.

4.2 Analysis Set

ECG and ECHO data will be analyzed using the Safety Population, including all randomized subjects who received at least one dose of study medication. The analyses will be based on the actual treatment taken.

No comparisons between sites will beconducted.

4.2.1 Handling of Missing Data

All data available will be used for the analysis. Missing data points will not exclude the rest of the subject's data from analysis, and missing data will not be imputed.

4.3 Interim Analysis

No interim analysis is planned for this study.

4.4 Multiplicity Adjustments

No adjustments for multiplicity will be made for the cardiovascular endpoints.

4.5 Primary Analyses

4.5.1 Electrocardiogram

The primary ECG objective is to evaluate the effect of ZX008 0.8 mg/kg/day (max 30 mg/day) on QTcF.

Justed

Just The primary analysis of the OTcF isthemean baseline- and placebo-adjusted difference at each time-point and will be performed using an analysis of variance (ANOVA) model with an effect for treatment for each post-dose time point. The upper bound of the one-sided 95% CI (or, equivalently, two-sided 90% CI) of the mean placebo- and baseline-adjusted difference for QTcF ($\Delta\Delta$ QTcF) will be calculated from the least square mean differences of the ANOVA for each time point.

The general formula to calculate the $\Delta\Delta$ QTcF at the *i*th timepoint is:

